Smoking cessation interventions for cancer patients also need to address psychological distress (Cataldo et al., 2010; de Moor et al., 2008; Gritz et al., 2006; 2007) and cognitive impairment (Cox et al., 2003). A cancer diagnosis and its medical treatment can lead to clinically significant and protracted symptoms of psychological distress and cognitive impairment (Biegler et al., 2009; Pirl et al., 2004). Psychological distress among cancer patients typically involves symptoms of depression and anxiety (Kash et al., 2005; Holland & Alici, 2010), while cognitive impairment typically includes difficulties with memory, attention/concentration, and executive function (Biegler et al., 2009). Symptoms of psychological distress have been shown to be a strong risk factor for relapse following successful smoking cessation in the general population (Zvolensky et al., 2009) and among cancer patients ([name] et al., 2010a). Likewise, in the general population, smokers use nicotine to enhance

cognitive function, nicotine withdrawal increases cognitive impairment which predicts relapse, and resuming smoking ameliorates abstinence-induced cognitive impairment (Heishman, 1999; Evans & Drobos, 2009; Rukstalis et al., 2005). A higher level of cognitive impairment among cancer patients has also been associated with a greater likelihood of smoking (Kahalley et al., 2010).

Lastly, to date, smoking cessation clinical trials for cancer patients have inadequately considered the protracted time-line for smoking relapse exhibited by cancer patients relative to the general population of smokers (Gritz et al., 2006; 2007). In the general population of smokers, the large majority of smokers who achieve abstinence and relapse do so within 1-2 weeks (Shiffman, 2006). A meta-analysis of studies with the general population of smokers showed that, after abstinence, upwards of three-quarters of individuals relapse within 8 days from abstinence (Hughes et al., 2004). In contrast, studies with cancer patients illustrate a delayed or protracted relapse process. A prospective study of smoking behavior among head and neck cancer patients showed that the majority of relapse to smoking occurs within 6 months following initial abstinence (Gritz et al., 1999). Likewise, prospective studies with lung cancer patients reported that the majority of smoking relapse did not occur until 2 months after initial abstinence (Cooley et al., 2009; Walker et al., 2006).

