Aim 3: The analyses will assess changes in affect and cognitive impairment as mediators of treatment arm effects at Week 24 and 52. These measures are continuous difference scores. Our sample of 374 is well above the minimum sample of 200 recommended for models of this size (Haduk, 1987; Boosma & Gabrielli, 1985). The mediation hypothesis will examine the proportion of treatment effect explained (Lin et al., 1997; Vittinghoff et al., 2009), and test with a z-score generated using the delta method. Our sample of 374 gives us 80% power to observe small effects in a 1-sample test ($\delta=0.20$) when testing at $\alpha=0.05$. There are two proposed mediating pathways between treatment and outcome, so our type-1 error will be corrected to 0.025. Our sample of 374 gives us 80% power to detect small to medium effects ($\delta=0.22$) for changes in the proposed mediators.

[figure not shown]
Data Analysis

[name] will oversee analyses. Preliminary analyses will assess sample characteristics by treatment with chi-square or logistic regression (e.g., gender, dependence, depression, disease site). These variables will also be examined for their relationship to completion of outcome assessments. Variables related to treatment arm and completion of follow-ups will be included as covariates in analyses of study aims. Compliance measures will be evaluated across treatment arms, and controlled for in primary analyses. Although we will use an intent-to-treat analysis as the primary method for evaluating study aims, we will conduct a completers only analysis of study aims and examine study aims with participants lost to follow-up due to death excluded as done previously ([name] et al., 2003).

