Aim 3: Assess changes in affect and cognitive impairment and cue-elicited urges as mediators of extended varenicline therapy's effect on quit rates. The effects of treatment arm on mediators will be assessed using linear regression. Structural equation modeling will be used to obtain a more comprehensive understanding of these mechanisms. It is hypothesized that treatment arm will yield significant differences in proposed mediators and that differences in mediators will predict week 24 and 52 outcomes. We will focus on changes in mediators from baseline to week 14, when the standard therapy participants transition to placebo and the extended therapy group stay on active treatment. After first demonstrating that treatment arm affects quit rates (Aim 1), these effects will be partitioned into mediated and unmediated effects, via path and structural equation models. For example, paths *d* and *b* represent the mediated effects of treatment arm on quit rates through changes in negative affect, and path *a* represents residual effect of treatment arm on quit rates not mediated by negative affect. Path *f* represents the hypothesis that the impact of treatment arm on quit rates will depend on negative affect. Specific hypotheses will be tested by using chi-square difference tests that contrast the overall fit of this full model with more parsimonious nested models in which specific predictive effects are fixed to zero (e.g., the unmediated path *a*). Model goodness-of-fit indices will be contrasted to guide interpretation of results and determine the practical significance of statistically significant differences. Modification indices will be examined to guide model interpretation and modification. Models will be tested through Mplus, which easily accommodates the combination of binary and continuous variables. This approach allows us, in principle, to test whether treatment effects on quitting are due to specific mechanisms (e.g., reduction in negative affect). Tests for mediation by positive affect, withdrawal, cognitive impairment, and cue-elicited urges will be conducted in this fashion.

Path Model of Treatment Arm, Negative Affect, & Quit Rate

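### Aim 3 estimates the mediator-to-quit path without adjusting for smoking status, so the mediated share is confounded, in a direction the documents do not fix

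*Combined protocol and SAP*

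**What the plan says.** In the Statistical Analysis section, Data Analysis, Aim 3, the mediator is a change score: "We will focus on changes in mediators from baseline to week 14". The treatment effect is split into a residual path *a* and two paths, *d* and *b*, that "represent the mediated effects of treatment arm on quit rates through changes in negative affect". Aim 3 expects that "differences in mediators will predict week 24 and 52 outcomes". Positive affect, withdrawal, cognitive impairment and cue-elicited urges are handled in the same way. The stated purpose is causal: "This approach allows us, in principle, to test whether treatment effects on quitting are due to specific mechanisms".

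No smoking-status term for Week 12 or Week 14 is named in either equation. The opening paragraph of Data Analysis gives the general covariate rule: "Variables related to treatment arm and completion of follow-ups will be included as covariates in analyses of study aims". It adds one post-randomisation adjuster: "Compliance measures will be evaluated across treatment arms, and controlled for in primary analyses". FTND and HADS appear under the screening and covariate heading of Table 2, and the Depression and Anxiety paragraph gives HADS both roles, mediator and covariate. The plan states no assumption about mediator-outcome confounding and no sensitivity analysis for it.

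Under Power, the mediation test is a delta-method z for the proportion of treatment effect explained, with alpha reduced to 0.025. Aim 3 also describes chi-square tests of single paths in nested models. The split is to follow a demonstrated Aim 1 effect.

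**The concern.** Arm is randomised; the mediator is not. A variable that influences both the Week 14 mediator and Week 24 abstinence will make path *b* non-zero even if the mediator does nothing. Smoking status is such a variable on the protocol's own evidence. The Background section on barriers to quitting says that "resuming smoking ameliorates abstinence-induced cognitive impairment", and the Withdrawal paragraph under Potential Study Risks lists low mood, anxiety, irritability and poor concentration in people who quit. A patient who is abstinent when the arms diverge is also far likelier to be abstinent at Week 24.

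The change score adds to the problem. Both arms take the same active drug through Day 84, so 12 of the 14 weeks it spans come before any difference in treatment. Change over those weeks cannot carry an arm effect, yet it enters path *b* along with whatever quitting or continued smoking did to the mediator.

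At stake is the Aim 3 conclusion about mechanism. The Aim 1 comparison of quit rates is not affected.

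**Working it through.** **Plan's own figures.** A comparison of 33% with 47%, 187 per arm, has 79.2% power at two-sided 0.05, which agrees with the stated 80%. (The Aim 3 power statement does not reproduce: Φ(0.20·√374 − 1.96) = Φ(1.91) = 97%, not 80%. That is a separate matter and nothing below depends on it.)

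**Inputs from the documents.** N = 374; Week 24 quit rates 33% and 47%; alpha 0.025 for mediation, two-sided; Aim 1 demonstrated first at 0.05; arms identical until Day 85; a mediator effect of 0.22 SD from the Aim 3 power text.

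**Assumed inputs.** 1:1 allocation; 45% abstinent at Week 12 in both arms; an abstainer-smoker gap on the mediator of g = 0.2, 0.3 or 0.5 SD; an alternative arm effect of 0.32 SD; Week 24 abstinence of 60% (standard) and 85% (extended) among Week 12 abstainers, and 11% and 16% among Week 12 smokers. These give the plan's rates:
- standard: 0.45 × 0.60 + 0.55 × 0.11 = 0.33
- extended: 0.45 × 0.85 + 0.55 × 0.16 = 0.47

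**Model.** Mediator M = d·arm + g·(Week 12 abstinent) + N(0,1). Week 24 abstinence depends on arm and Week 12 status only. M has no effect on it, so true mediation is zero.

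**Tests.** Path *d* comes from linear regression of M on arm. Path *b* comes from logistic regression of abstinence on arm and M. The path test is b/se(b). The delta-method z is taken on the product of the two paths, standing in for the proportion explained: z = d̂b̂ / √(d̂²·se(b̂)² + b̂²·se(d̂)²). Both are two-sided at 0.025. The Aim 1 precondition was met in about 80% of simulated trials.

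**Results (share of trials rejecting; true mediation zero).**

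| Gap g | Path test, unadjusted | Delta z with Aim 1 precondition, d = 0.32 | Same, d = 0.22 | Path test, adjusted for Week 12 status |
|---|---|---|---|---|
| 0 | about 2% | under 1% | under 1% | 2–3% |
| 0.2 SD | 13–15% | about 2% | about 1% | 2–3% |
| 0.3 SD | about 29% | about 6% | 2–3% | 2–3% |
| 0.5 SD | about 72% | about 20% | about 8% | 2–3% |

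Where ranges are shown, repeat simulations differed by that much. With no gap the error is at or below nominal, so the excess comes from the omitted smoking status.

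**Direction.** With abstainers 0.3 or 0.5 SD worse instead of better, the path test rejects about as often (about 30% and 73%), but every rejection has the negative sign, opposite to the Aim 3 hypothesis.

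**Residual bias.** The adjusted column assumes no relapse between Weeks 12 and 14. In a second set of scenarios, with relapse of 15% (standard) and 5% (extended) over those weeks and gaps of 0.3 to 0.8 SD, adjustment for Week 12 status leaves the path test at 4–12%; adjustment for Week 14 status brings it to about 2–3%.

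**The case against.** The strongest reply concerns direction. A reader might infer that the trial will tend to report mediation by affect whether or not it exists. The documents do not support that. The Background and Withdrawal passages describe people who quit as worse on cognition and mood. If that persisted to Week 14, the spurious path would run against the hypothesis and could mask real mediation. A positive bias needs abstainers to score better, for which these passages give no evidence. This objection stands.

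Size is also open. The Withdrawal paragraph says symptoms are mostly mild and last 1–2 weeks. With quit day at Week 1, long-term abstainers may be past them by Week 14 and the gap could be small. A criterion requiring both paths to be significant gives higher rates, roughly 10, 24 and 56% at an arm effect of 0.32 SD. The plan names a delta-method z and an Aim 1 precondition, so those rates should not be attributed to it. The single-path tests, however, are in the plan and remain inflated.

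Some adjustment is already provided. FTND and HADS are designated covariates and compliance is controlled for, but none of these is smoking status. The path figure is not reproduced in the text available, and paths *c* and *e* are not described, so an adjuster drawn there cannot be excluded. The caption names only treatment arm, negative affect and quit rate.

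Finally, the protocol says "nicotine withdrawal increases cognitive impairment which predicts relapse", so a real mediator effect is plausible and part of the path may be genuine. That argues for separating the two influences.

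**Conclusion.** The point holds as one of confounding with unknown direction. As written, the mediator-to-quit path absorbs the effect of smoking status, and the split into mediated and unmediated effects is biased whenever abstainers and smokers differ on the mediator at Week 14. For a 0.3 SD gap, the single-path test would reject in about 29% of trials with no true effect; the delta-method z with the Aim 1 precondition would reject in about 6% or 3%, depending on the arm effect. These figures rest on the assumed gap, the assumed Week 12 abstinence and the assumed dependence of Week 24 on Week 12 status, none of which the documents give.

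A reader might also conclude that the causal claim fails outright. That goes too far: the plan hedges it as holding in principle, and adjustment with data already scheduled removes most of the problem. This should be changed before analysis. It does not threaten the primary comparison.

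**What to change.** In both the arm-to-mediator and the mediator-to-quit equations, include:
- smoking status fixed before Day 85, from the Week 12 timeline follow-back, with CO where available;
- the Week 12 value of the same mediator, where that mediator is measured at Week 12;
- baseline FTND and HADS, already listed as covariates.

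Use the same covariates in the model for the total effect, so that the split compares like with like on the logit scale. Values that precede Day 85 cannot be affected by arm, so adjusting for them blocks no treatment effect. Because the Week 12 visit window is plus or minus one week, take status from the daily follow-back record at a fixed date, and confirm that the Week 12 mediator value precedes the switch.

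Report a sensitivity analysis for residual mediator-outcome confounding, for example adding Week 14 follow-back status. Keep that out of the main model: Week 14 status follows the divergence and may be affected by arm or by the mediator. Limit the wording on specific mechanisms in Aim 3 accordingly.

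The cost is SAP wording and a little more analysis, with no new data: affect, cognition, withdrawal, urges and smoking status are all scheduled at Week 12. The resulting mediation claim will be more cautious.

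### With path f in the Aim 3 model, path a is the arm effect only at a mediator value of zero, so neither its reading as the overall unmediated effect nor its nested test stands as written

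*Combined protocol and SAP*

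**What the plan says.** The section is 2. Statistical Analysis, Data Analysis, Aim 3. Once Aim 1 has shown an arm effect on quitting, "these effects will be partitioned into mediated and unmediated effects, via path and structural equation models". Negative affect is the worked example:

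- For d and b together, the text says that they "represent the mediated effects of treatment arm on quit rates through changes in negative affect".
- For a, it says that this path "represents residual effect of treatment arm on quit rates not mediated by negative affect".
- For f, it says that this path "represents the hypothesis that the impact of treatment arm on quit rates will depend on negative affect".

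Hypotheses are tested by chi-square differences that "contrast the overall fit of this full model with more parsimonious nested models in which specific predictive effects are fixed to zero". The nested model named as the example fixes path a. The same text is repeated after the path-model caption, and the approach is to be reused for positive affect, withdrawal, cognitive impairment and cue-elicited urges.

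On the scale of the mediators, the Aim 3 power paragraph says "These measures are continuous difference scores", and the analysis paragraph says "We will focus on changes in mediators from baseline to week 14". The power paragraph also plans to examine the share of the treatment effect explained, with a delta-method z test.

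The plan does not state any centring or reference value for the mediator, whether f is also fixed when a is fixed, or how the mediated effect is defined when f is not zero.

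**The concern.** Path f makes the arm effect vary with negative affect. Once that is allowed, there is no single arm coefficient that is the residual effect. The coefficient called a is the arm effect at one value of the mediator, namely wherever its zero lies. Fixing a to zero while f stays free therefore tests a statement about participants at that value, not about the trial population.

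If f acts through the week-14 change, there is a second consequence. Path b is then the affect slope in the reference arm only, so d and b describe the mediated effect in that arm only.

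At stake is the main output of Aim 3, the split of the treatment effect into mediated and unmediated parts. A weak test of path a favours the simpler model without a direct effect, and so a reading in which affect carries more of the benefit than it does. The structure is shared by all the mediators.

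**Working it through.** The plan gives no figure to reproduce here, so the check is algebra followed by simulation.

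**Algebra.** Write the outcome part of the model as logit P(quit) = i + a·Arm + b·M + f·Arm·M. Replace M by M − c. The fit, b and f are unchanged, but the arm coefficient becomes a + f·c. It is free of c only if f = 0. With 0/1 arm coding, and on the linear-predictor scale, the mediated effect is d·b in the reference arm and d·(b + f) in the other.

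**One simulated trial** (374 participants, true a = 0.4, f = -0.4). The estimates were a = 0.456 and f = -0.338, and the log-likelihood was -239.4065 at every origin.

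| Zero of M moved by | Arm coefficient | p for a = 0, f free |
|---|---|---|
| -1 SD | 0.456 + 0.338 = 0.794 | 0.0045 |
| 0 | 0.456 | 0.044 |
| +1 SD | 0.456 − 0.338 = 0.118 | 0.75 |

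The data and the fit are the same in each row. Reversing the arm coding moves b from -0.391 to -0.728, which is b + f up to rounding.

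**Rejection rates at the planned size.**

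- From the Aim 1 power paragraph: quit rates 33% and 47%, and n = 374.
- Assumed, not in the documents: 187 per arm, M in SD units, d = -0.32, b = -0.4, control-arm mean change -0.5.
- The intercept and a are solved to give the two quit rates.
- The overall mean of M is -0.5 + (-0.32)/2 = -0.66.
- The test is the likelihood-ratio test of a = 0 with f free, at the two-sided 5% level. The plan's corrected Aim 3 level is 0.025, at which every rate would be lower.

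| True f | Zero at no change | Zero at control mean | Zero at overall mean |
|---|---|---|---|
| -0.3 | 13% | 38% | 48% |
| 0, but f left in | 43% | 59% | 61% |

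For f = -0.3 the solved a is 0.227 at no change. At the overall mean it is 0.227 + (-0.3)(-0.66) = 0.425. The test at no change is therefore of a smaller quantity, estimated away from the centre of the data. In the second row the quantity is the same at every origin, and only the loss of precision away from the centre remains. It costs 61 − 43 = 18 percentage points of power.

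**What the direct effect is when f = -0.3.** The 14-point difference splits in two legitimate ways:

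- Pure direct 9.0 points plus total indirect 14 − 9.0 = 5.0 points, a mediated share of 5.0/14 = 0.36.
- Total direct 11.2 points plus pure indirect 14 − 11.2 = 2.8 points, a mediated share of 2.8/14 = 0.20.

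The plan's wording does not choose between them.

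**Testing f first.** In the f = -0.3 scenario, a 5% test of f detects it in about 25% of trials.

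**The case against.** Four points can be made for the plan.

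- **The diagram is not shown, so f is read from the prose.** This stands in part. The prose ties d and b to changes in negative affect, but ties f only to negative affect. If f uses the level of affect, b is not specific to an arm and the point about d and b falls away. The dependence of path a on the zero point remains in either case.
- **A difference score has a natural zero.** This stands, and it limits the concern. A reader might infer that the verdict on path a can be moved at will by choosing any zero, even the bottom of the scale. The documents do not support that: if f acts through the change, the raw zero is no change. Path a then has a meaning, but it is the arm effect for a participant whose affect did not change, not the overall residual effect the plan describes.
- **The plan never says that a non-significant path a means full mediation.** This is correct. Fit indices are also to guide interpretation, so a reader who infers an automatic declaration of full mediation goes too far. The nested test of a is still the plan's named example and still feeds that interpretation.
- **The share explained need not be distorted.** A reader might infer that the reported share will be badly wrong. The plan gives no formula for it. At f = -0.3 the simple ratio d·b/(a + d·b) is 0.128/(0.227 + 0.128) = 0.36, which agrees with one of the two natural splits. The defect is that the share is undefined when f is not zero, not that it is known to be wrong.

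**Conclusion.** The concern holds for Aim 3. With f free, path a is the arm effect at a mediator value of zero, and its nested test does not address the overall residual effect. That follows from algebra and needs no assumption beyond reading f as an interaction in the full model. If f uses the week-14 change, d and b also give the mediated effect in the reference arm only.

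The size rests on assumed paths: rejection of a = 0 in about 13% against 48% of trials when f = -0.3, and 43% against 61% when f is zero but left in, comparing zero at no change with zero at the overall mean. Other path values, or a control-arm mean change nearer zero, would give other gaps. The dependence on the zero point disappears if f is dropped, or is fixed together with a, but the plan specifies neither. The Aim 1 comparison is untouched.

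**What to change.** In the Aim 3 analysis text, and in its repetition after the path-model caption:

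1. Define f in words, and state whether it multiplies arm by the week-14 change or by a level of affect, and at which visit.
2. Centre the mediator at its overall mean before forming the arm-by-affect term, and describe a as the arm effect at average affect.
3. Whenever f is in the model, take the mediated and unmediated parts and the share explained from natural direct and indirect effects on the quit-rate difference scale, not from a and d·b. Name the decomposition in advance, for example pure direct plus total indirect, and give bootstrap intervals.
4. Do not make step 3 depend on a significance test of f. With about 25% power in the scenario above, such a test would usually drop a real interaction and restore the readings at issue.

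Apply the same text to the other mediators. The cost is a change of wording and slightly more analysis; no new data are needed.
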